BACKGROUND	
Renal denervation (RDN) is a recent procedure that can be used to control BP (blood pressure) in hypertensive patients. Numerous publications from randomised trials have demonstrated the efficacy of RDN in this indication (1-14). The latest guidelines now include RDN as an effective technique for use in hypertension. Since the beginning of 2023, RDN using Medtronic's Spiral radiofrequency system has benefited from transitional authorisation for reimbursement by the French health insurance system. An application for reimbursement is underway for the ultrasound system.
 
We aim to compile an exhaustive prospective register of all procedures carried out in France over the next few years, regardless of the type of catheter used or the context in which the procedure was carried out (transitional reimbursement, industrial register, randomised trial). Our aim is to assess the efficacy and safety of the procedure within the French healthcare system, the characteristics of patients benefiting from the procedure, the centres performing renal denervation, and the care pathways used, and to be able to present all this data, independently of the industry, to the healthcare authorities when it comes time to reassess the value of this procedure and its indications.

PRIMARY OBJECTIVE	 Diagnostics  Prevention and treatment  Patient management  Patient safety  Organization of healthcare facilities  Public health policies  Understanding diseases  Other: To describe changes in SBP evaluated in Home Blood Pressure Measurement (HBPM) in hypertensive patients between before and 1 year after treatment with RDN.
PRIMARY ENDPOINT	Change in SBP measured by HBPM before and after RDN (1 year).

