	
● Procedure:
- Indication validated by a Centre of Excellence or Blood Pressure Clinic (yes/no)- Complete secondary hypertension work-up (yes/no)- In particular: plasma renin/aldosterone assay? Methoxylated catecholamine derivatives? renal artery imaging?- Precise indication of the procedure- context of treatment (temporary reimbursement of SIMPLICITY catheters, registry, randomised study)- specialities of the doctor(s) performing the procedure,- details of the procedure: under general anaesthetic/analgesia, approach,- Antithrombotics and anti-platelet aggregants before, during and after the procedure- number of ablation/sonication points performed- volume of contrast medium used, X-ray dosimetry- closure system for the approach port- complications, if any● Follow-up data :
- Date and type of follow-up- Progress of treatment- clinical BP measurements, MAPA and self-measurements performed- Changes in biological markers- Changes in imaging of the renal arteries- Complications, if any 
This might include retrospective data for patients treated with RDN in the past, if investigator believe that the missing data are absent or scarce. As we will collect only data coming from a routine care already widely used in France for these patients, this should correspond to most of the patients already treated with RDN. Patients included retrospectively and prospectively will be compared to ensure that there are no selection biaises in the retrospective cohort.
 
Use one or more of the following sensitive variables :
 
 Country and department of residence of the person studied (NB: the collection of the commune of residence (zip code and/or name) is not permitted) Pays et département de résidence de la personne étudiée (NB : le recueil de la commune de résidence (code postal et/ou nom) n'est pas autorisé)
 
 Year and month of birth

--	---

	 Date of care (DDMMYYYY)  Date of death (DDMMYYYY)  City of death  None
ORIGIN OF DATA	 Medical record  Survey / Cohort / Register not including SNDS data  Other data

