	 Data from the investigator's department only (coordinating and associated centers)  Data from several departments of the CHU Grenoble Alpes or from a department other than that of the investigator (if the investigator is at no time involved in the care of the persons targeted by the research).
DATA COLLECTION SCHEDULE	
Prospective and retrospective research :
 
 - 3-year register (start of collection april 2025 - end of inclusions april 2027, follow-up : 1 year) 
For retrospective patients, data collection will be done from clinical database from january 2010. A 4-week delay must be observed between the sending of information letters and the start of data collection.
 
 - End of follow-up: april 2028. - Annual analysis of data from patients who have undergone RDN and follow-up at 1 month, 6 months, 1 year after the procedure.
DATA COLLECTION	
Collection :
 
The data collected will be those from routine follow-up at 1 month, 6 months, 1 year of all patients benefiting from a RDN procedure and included in the registry. After the procedure, the investigator in each participating centre will manage the follow up of the patient. As the study is purely observational, it does not require any specific follow-up visits, but includes the collection of data obtained during routine follow-up visits. The registry does, however, include data collection at fixed times after procedure. The data reported in the Redcap file will be the data available closest to the theoretical day of collection.
 
Patients who have been lost to follow-up should be investigated through the referring doctors to RDN and/or by family members or any other person whose name appears on the patient liaison form. In the absence of any information, a search for the patient's possible death will be carried out by consulting the https://deces.matchid.io/searchqui website, including the INSEE source for deaths (the search will be carried out by birth name).
 
In case of the patient's death, the medical record is first checked to ensure that the patient has "no objection" to the use of his or her health data for research purposes.
 
Clinical data collection will be based on the source documents.

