	
Codage :
 
The data will be pseudonymised by coding: patients will be identified as follows: centre number followed by a hyphen (-) then the patient number coded number specific to the research indicating the order of inclusion of subjects (ex. 01-001). The list of correspondences between the patient code and his identity will be kept in each participating center, in the service server, by the investigator on an Excel file.

DATA STORAGE PERIOD	
Personal data relating to persons taking part in research, and processed for this purpose, may be kept in the information systems of the controller, the participating centre or the healthcare professional involved in the research for a maximum of 2 years after the last publication of the results of the research or, if there is no publication, until the final report of the research is signed.
 
The personal data of the professionals involved in the research may not be kept for more than fifteen years after the end of the last research project in which they participated.
 
It is then archived on paper or electronically for a period of time in accordance with the regulations in force. The data must then be deleted.

DESCRIPTION OF STATISTICAL ANALYSIS OF DATA	
NUMBER OF SUBJECTS TO BE INCLUDED
 
The number of subjects included will correspond to the number of patients undergoing renal denervation for hypertension at the Grenoble University Hospital and in the various French centres participating in the study during the study period (the estimation is currently 100 per year).
 
DATA ANALYSIS
 
The database will be stored in accordance with the signed investigator commitment, on a secure database certified to keep health data, and linked to the REDCAP system supporting the eCRF. The analyses will be carried out at the University Cardiology Clinic of the Grenoble University Hospital by [name] and [name] with the help of the SFHTA, using SPSS version 21 (SPSS Corp, Somers, NY) and STATA® 14.1 (Stata Corporation, College Station, TX).

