	
Statistical analysis: Absolute values, percentages and means (SD) will be calculated to describe the population.
 
The differences between the variables before and after the RDN will be tested using either a paired t-test for normally distributed data or a Wilcoxon test, and a paired Chi2 or a Fisher test. For univariate analysis of variables between the RDN responder groups (5 mmHg reduction in 24h SBP) and non-responders, we will use the t-student analysis of variance test or non-parametric tests for continuous variables, and chi2 or Fisher tests for categorical variables. A multivariate analysis will also be performed.

PEOPLE INCLUDED IN THE RESEARCH	
Number of subjects: Estimation of 100 per year (might be less in the first year, then more as RDN implementation in France increase)
 
Inclusion criteria: Adult (> 18 years old) hypertensive patients treated with RDN in France whatever the catheter and the indication. This might include retrospective data for patient already treated with RDN in the past.

	
Non-inclusion criteria: RDN not proposed to the patient, patient opposing the collection and use of his/her data for research purposes.
 
Information and traceability procedures for non-objection/opposition :
 
Patients will be fully and fairly informed, in comprehensible terms, of the objectives of the study and the nature of the information collected, and of their right to object at any time to the use of the data collected. They will be given an information letter and the non opposition will be written down in the medical records of the patient. If the subject objects to their personal health data being processed for research purposes, this objection will be recorded in their medical file. This right of objection may be exercised at any time by any means with either the person responsible for the research or the establishment holding the data, which undertake to respond to the request within a maximum of 2 months.
 
Retrospective patients will be informed by post. On receipt of this letter, the patient will have 4 weeks to object.

ETHICS	NA

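### Past patients enter on the investigator's judgement of data completeness, the eligibility criteria omit that condition, those left out are not counted, and the planned comparison cannot exclude selection bias

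*Protocol*

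**What the plan says.** The protocol's BACKGROUND sets the aim: "We aim to compile an exhaustive prospective register of all procedures carried out in France over the next few years". METHODOLOGY also allows retrospective use of routine data, and DATA COLLECTION SCHEDULE fixes how far back it goes: "For retrospective patients, data collection will be done from clinical database from january 2010".

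TYPE OF DATA COLLECTED attaches a condition to past patients. They may enter "if investigator believe that the missing data are absent or scarce". It expects that "this should correspond to most of the patients already treated with RDN", and it names one safeguard: "Patients included retrospectively and prospectively will be compared to ensure that there are no selection biaises in the retrospective cohort".

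PEOPLE INCLUDED IN THE RESEARCH, which holds the eligibility criteria, mentions past patients without any condition on completeness: "This might include retrospective data for patient already treated with RDN in the past". The only non-inclusion grounds listed there are that denervation was not proposed or that the patient objects.

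DATA COLLECTION says "Patients who have been lost to follow-up should be investigated through the referring doctors to RDN" and adds a search of a public death database. It does not limit this to one cohort.

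**The concern.** The entry condition is a belief. The protocol does not say which variables or visits must be complete, how much may be missing, or when the judgement is made. For a patient treated years ago, the 1-year result, or its absence, may already be in the record when the investigator decides. Entry can then depend on follow-up and, through it, on outcome. Prospective patients face no such condition at entry.

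Under EXPECTED BENEFITS, the registry is meant to inform reimbursement decisions and the choice of indications. A past cohort assembled by discretion and without a denominator could colour both the blood pressure and the complication results. Readers could not judge by how much.

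**Working it through.** The protocol gives no figure on this point, so there is nothing to reproduce. The check has two parts: comparing the sections, and asking what the planned comparison can identify.

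**Who enters.**

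| | TYPE OF DATA COLLECTED | PEOPLE INCLUDED IN THE RESEARCH |
|---|---|---|
| Past patient, complete record, no objection | may enter | may enter |
| Past patient, incomplete record, no objection | depends on the investigator's belief | may enter |

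The sections differ in the second row. No section asks centres to count past patients treated, contacted, objecting or not entered, so the expectation of covering most of them cannot be checked. Tracing and the death search act on patients already in the registry. They cannot recover a past patient who was never entered.

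**What the comparison can identify.** Let q be the share of past patients left out. For any outcome mean:

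- mean(all past) = (1 − q) × mean(entered) + q × mean(left out)
- hence mean(entered) − mean(all past) = q × [mean(entered) − mean(left out)]

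This identity is exact. The plan records neither factor. The planned comparison observes

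- mean(entered past) − mean(prospective) = q × gap + [mean(all past) − mean(prospective)]

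The second term carries calendar period (from 2010 against April 2025 to April 2027) and any change in case mix. One observed difference cannot separate two unknown terms. A selection shift of −3 mmHg and a period difference of +3 mmHg would give zero. Procedure date, indication and context are collected, so adjustment for them is possible, but no adjustment sees patients who were not entered.

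**Illustration for 1-year home systolic pressure change.** A past patient without paired readings cannot contribute to this mean under any entry rule. So q here is the share left out among past patients who do have paired readings. The protocol's expectation about most patients does not bound that share. Assumed inputs:

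- q from 0.10 to 0.50
- gap from 2 to 6 mmHg, in either direction
- SD of change 15 mmHg (range 10 to 20)
- 50, 100 or 200 past patients
- 200 prospective patients, from the stated 100 per year × 2 years of inclusion, all with paired readings

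Shift in the retrospective mean: 0.10 × 2 = 0.2 mmHg up to 0.50 × 6 = 3.0 mmHg.

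95% CI half-width of the cohort difference = 1.96 × SD × √(1/n + 1/200):

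| Past patients n | SD 10 | SD 15 | SD 20 |
|---|---|---|---|
| 50 | 3.10 | 4.65 | 6.20 |
| 100 | 2.40 | 3.60 | 4.80 |
| 200 | 1.96 | 2.94 | 3.92 |

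At SD 15, shifts of this assumed size lie almost entirely within the comparison's own uncertainty. At SD 10 with 100 or 200 past patients, the larger ones would exceed it. Even then, the comparison could not say whether selection or period caused the difference.

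**The case against.** The sponsor saw the risk and planned a comparison, which remains useful as description. Both sections say only that past data might be included, so the mismatch can be read as an unrepeated condition in a short document. The variables and test for the comparison, any pooling, and the choice of primary cohort can sit in an analysis plan that is not shown. Every input to the illustration is assumed.

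Much of this stands, and it rules out three stronger readings.

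- A reader might infer that past patients who died or were lost are dropped while prospective ones are traced. The protocol does not say so. Tracing and the death search cover any patient in the registry, date of death is a collected variable, and deceased patients' records are to be checked for non-objection. The asymmetry is at the entry step only, and exclusion after death is a possible reading of the rule, not a required one.
- A reader might take the 0.2 to 3.0 mmHg as the bias in the primary result. The protocol supplies none of its drivers and does not say that the cohorts will be pooled. A new entry rule changes nothing in that mean for patients without paired readings.
- A reader might conclude that the prospective cohort must be primary or the look-back shortened. Those are design preferences or matters for the analysis plan.

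The objection does not remove the core. The entry rule and the accounting for those left out belong in the protocol, because analysis cannot undo selection made when records are chosen.

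**Conclusion.** The point holds, and it should be fixed before centres select past records. The rule permits discretionary entry with follow-up on file, the eligibility criteria do not carry it, nobody counts those left out, and the stated check cannot deliver the assurance claimed for it. These conclusions rest on the text alone.

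The text shows that selection related to outcome is possible and would go unseen, not that it will occur. Its sign and size are unknown. For 1-year home systolic pressure change, the rule matters only for past patients who have paired readings and would be left out for other gaps or by discretion. For everyone else, what is at stake is the denominators and the reporting of complications and deaths.

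**What to change.** 1. Under both TYPE OF DATA COLLECTED and PEOPLE INCLUDED IN THE RESEARCH, replace the belief condition with one rule that does not depend on follow-up or outcome. Suggested text: all consecutive past patients at each participating centre since January 2010 with a documented renal denervation procedure and no objection are entered, whatever the completeness of their data; death, loss or missing follow-up is not a reason for non-entry.
2. Report per centre, as aggregate counts, the past patients treated, contacted, objecting, entered, and with paired 1-year home readings, with reasons for non-entry.
3. Reword the purpose of the cohort comparison as describing differences, with estimates and 95% CIs. Show retrospective and prospective results separately alongside any pooled result.

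The cost is wording in two sections, a list of past procedures at each centre, some additional information letters with their 4-week wait, and further record abstraction. Missing data will look worse, because they will now be visible.

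### Follow-up closes, to the month, 12 months after the last inclusion, so a 1-year home SBP reading taken shortly after month 12 counts for earlier patients but not for the last ones

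*Protocol*

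**What the plan says.** The Data Collection Schedule section of the protocol describes a 3-year register and gives its calendar as "start of collection april 2025 - end of inclusions april 2027, follow-up : 1 year". It then states "End of follow-up: april 2028".

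The primary endpoint is the change in home SBP from before the procedure to 1 year after it. The Data Collection section leaves the timing of that reading to usual care: as the study is observational, "it does not require any specific follow-up visits, but includes the collection of data obtained during routine follow-up visits". It assigns readings to time points by proximity: "The data reported in the Redcap file will be the data available closest to the theoretical day of collection". It states no window or maximum distance from the target day.

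The study schedule marks home BP at 1, 6 and 12 months. It marks follow-up ABPM, renal artery ultrasound and angioCT at 12 months only, although the secondary objectives also name earlier time points. On accrual, the protocol gives an estimate of 100 patients per year and adds that it "might be less in the first year, then more as RDN implementation in France increase".

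**The concern.** Routine 1-year visits do not all fall on the anniversary; some are early and some late. The closest-reading rule handles this for most patients, because it can reach to either side of month 12. For patients treated in the last weeks to months of accrual, the end of follow-up removes the late side. A reading at month 13 lies outside the register as dated, which leaves an earlier reading or none.

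Two things are at stake. The 1-year value would be defined slightly differently for late and early patients. And because the closest-reading rule has no limit, the earlier reading that fills the gap could be the 6-month one. The 12-month ABPM and imaging are exposed to the same cut-off, and where a centre follows the study schedule they have no earlier follow-up value to fall back on. If accrual rises as the protocol expects, the affected months are also the busiest. An analysis plan can set a window, but it cannot bring back readings taken after follow-up has ended; that date is fixed in the protocol.

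**Working it through.** **1. The plan's own calendar.** April 2025 to April 2027 is 24 months of inclusion. Adding 12 months gives April 2028, or 36 months in all. This reproduces the stated 3-year register and the stated end of follow-up. No further collection period is described.

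**2. Margin for the last patient.** I take inclusion and procedure as simultaneous, since the study schedule places patient information during the hospitalisation for RDN. The dates are given only to the month:
- last inclusion 30 April 2027, close 1 April 2028: the close falls 29 days before the anniversary;
- both on the same day of the month: 0 days;
- last inclusion 1 April 2027, close 30 April 2028: 29 days after the anniversary.

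The margin is therefore nominally zero and lies between -29 and +29 days.

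**3. Patients whose 1-year reading falls after the close.** Let D be the delay of the reading beyond month 12, in months. A patient included t months before the end of inclusions is affected if D > t. With steady accrual, the expected number is

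accrual per month × E[max(D, 0)].

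For D normal with mean m and SD s, E[max(D, 0)] = s·φ(m/s) + m·Φ(m/s). The accrual of 100 per year (100/12 = 8.33 per month, 200 prospective patients over 24 months) comes from the protocol. The values of m and s, and the rate of 150 per year, are assumptions.

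| m, s (months) | E[max(D, 0)] | at 100/year | share of 200 | at 150/year in the last months |
|---|---|---|---|---|
| 0, 1.0 | 0.40 | 3.3 | 1.7% | 5.0 |
| 0, 1.5 | 0.60 | 5.0 | 2.5% | 7.5 |
| 1, 1.5 | 1.23 | 10.2 | 5.1% | 15.3 |

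**4. A second delay model.** If D is uniform on (-W, W), E[max(D, 0)] = W/4; if all readings are late, uniform on (0, W), it is W/2. At 100 per year:
- W = 0.5: 8.33 × 0.125 = 1.0 to 8.33 × 0.25 = 2.1 patients;
- W = 1: 2.1 to 4.2;
- W = 2: 4.2 to 8.3;
- W = 3: 6.3 to 12.5.

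This is 0.5% to 6.3% of 200, the same order as step 3.

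**5. Effect on the overall mean.** Suppose every affected patient had an earlier value entered, differing from the true 1-year value by 5 mmHg (assumption). The shift in the prospective mean is share × 5: 1.7% × 5 = 0.08 mmHg to 5.1% × 5 = 0.26 mmHg with the shares of step 3, and about 0.03 to 0.3 mmHg over the range of step 4.

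**6. With a 3-month margin.** Replacing m by m - 3 in the formula of step 3, the expected numbers at 100 per year fall to 0.0, 0.1 and 0.5 patients.

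**The case against.** The calendar is coherent: accrual plus nominal follow-up equals the stated duration, so there is no error or contradiction in the dates. That is right. This is a design choice that can be improved, not a mistake in the arithmetic.

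End of follow-up is also not the same as end of data entry. The data come from medical records, and the protocol gives no data-entry deadline, database lock or final-analysis date. Readings taken before April 2028 can be abstracted afterwards, and nothing stops the search for lost patients from running later. A reader might infer that this search has no time left for the last patients, but the protocol sets no deadline for it. What stands is narrower: a reading taken after the end of follow-up is outside the register as dated.

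A reader might also infer that the whole latest cohort loses its 1-year data. The figures do not support this: only patients from the last weeks to months of accrual whose reading happens to be late are affected. Retrospective patients treated well before the close, collected from January 2010, are untouched, so the share of the full registry is lower by an amount the protocol does not allow one to compute.

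Finally, one might read the protocol as saying that a 6-month value will serve as the 1-year value. It does not say so; its rule merely fails to exclude it. That gap applies to any patient without a reading near month 12, whenever treated, and moving the closing date alone would not cure it.

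**Conclusion.** The point holds as a minor one. To the nearest month there is no margin after month 12 for the last patients, while the date of the primary reading is left to routine care. About 3 to 10 prospective patients are affected at 100 per year, or roughly 2-5% of 200, and 5 to 15 if the last months run at 150 per year. The likely shift in the overall mean is a few tenths of a mmHg or less. The primary objective is descriptive, and no conclusion is shown to change.

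These sizes rest on assumed delays, on steady accrual and, for the shift in the mean, on an assumed 5 mmHg difference. The missing limit on the closest-reading rule is a separate cause: the closing date removes the late reading, and the open-ended rule permits a distant early one in its place.

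**What to change.** - Keep the end of inclusions at April 2027. Accept 1-year readings up to about July 2028 (12 months plus a 3-month margin), and state that the final 1-year analysis is run after that date.
- Limit the closest-reading rule to the same window around month 12, for example plus or minus 3 months, and treat readings outside it as missing. The 1-year value then has the same meaning for early, late and retrospective patients, and a 6-month reading cannot fill the slot.
- While amending, say when data entry closes.

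The cost is one later closing date and one added sentence on the window. The final analysis comes about 3 months later, and the register runs about 39 months (April 2025 to July 2028) instead of 36, so its description as a 3-year register needs updating. Some patients in any period will have a missing 1-year value where a distant reading might otherwise have been entered. No extra patients, visits or procedures are needed.

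### The rule of entering the reading closest to each follow-up time has no maximum distance, so an off-time home SBP can stand as the 1-year primary value

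*Protocol*

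**What the plan says.** The primary endpoint (Primary endpoint row of the protocol) is the change in home SBP from before RDN to 1 year after it.

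The Data collection section says how follow-up values are obtained:

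- Nominal times: "The data collected will be those from routine follow-up at 1 month, 6 months, 1 year of all patients benefiting from a RDN procedure".
- No mandated visits: the study is observational and "it does not require any specific follow-up visits, but includes the collection of data obtained during routine follow-up visits".
- A fixed timetable all the same: "The registry does, however, include data collection at fixed times after procedure".
- The selection rule: "The data reported in the Redcap file will be the data available closest to the theoretical day of collection".

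The Data collection schedule adds the calendar: "start of collection april 2025 - end of inclusions april 2027, follow-up : 1 year", and "End of follow-up: april 2028". It also opens the registry to past cases: "For retrospective patients, data collection will be done from clinical database from january 2010".

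Three other places bear on the point. The study schedule table marks home BP at 1, 6 and 12 months, without tolerances. The list of data collected includes the date of each follow-up, and it admits retrospective cases only where the investigator judges that little or nothing is missing. The statistical analysis section compares before with after by a paired t-test or Wilcoxon test and puts no timing condition on the after value.

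**The concern.** This is a positive instruction on what to put in the eCRF, so it is not merely a detail left open for a statistical analysis plan. In a registry that depends on routine care, some patients will have no home reading near month 12. For them the rule, as worded, points to whichever reading is nearest, however far away, and nothing tells the site to leave the field empty.

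Two things are at stake. First, the 1-year change would mix true 1-year values with values from other times, and the paired test would treat them alike. Second, a visit filled from another visit looks observed. Missing data are then understated, and a reading copied across visits looks like a stable effect. This also weakens the planned comparison of retrospective and prospective patients, because substitutes can lie much later in retrospective records, whereas a patient included at the end of recruitment can only have an earlier one. The registry is meant to inform reimbursement decisions, so the time at which the effect was measured matters.

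**Working it through.** The protocol gives no sample-size, power or variance figure, so there is no figure of its own to reproduce. The check applies the rule literally and then sizes a possible effect under stated assumptions.

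**1. The rule as a formula.** For each target t in {1, 6, 12} months, enter the reading r that minimises |r - t|. Targets are from the Data collection section; the reading patterns are examples.

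| Home readings available (months after RDN) | Entered at 1 | Entered at 6 | Entered at 12 |
|---|---|---|---|
| 1, 6, 12 | 1 | 6 | 12 |
| 1, 6 | 1 | 6 | 6 |
| 1 only | 1 | 1 | 1 |
| 9 only | 9 | 9 | 9 |
| 1, 22 | 1 | 1 | 22 |
| 1, 24 | 1 | 1 | 1 |
| 60 only | 60 | 60 | 60 |

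With readings on time the rule works. It misfires only when no nearer reading exists. For month 12, a 6-month reading (distance 6) is preferred to any reading after month 12 + 6 = 18, and a 1-month reading (distance 11) to any after month 12 + 11 = 23. A month-9 reading is 3 months from both 6 and 12.

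**2. How late a substitute could be.** From the stated calendar:

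- Prospective patient included in April 2025: at most 36 months of follow-up by April 2028, so at most 36 - 12 = 24 months late. The stated 1-year follow-up may rule out even this.
- Prospective patient included in April 2027: 12 months by April 2028, so no late substitute, only an early one.
- Retrospective patient treated in January 2010: up to 183 months of records by April 2025, or 219 by April 2028.

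Years-late values are therefore mainly a retrospective possibility.

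**3. Possible size, on assumptions only.** Let d1, d6 and d12 be the true mean changes, and f1 and f6 the fractions of patients whose 12-month value is filled from month 1 and month 6. Then

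error = f6 × (d6 - d12) + f1 × (d1 - d12).

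Assume d1 = -4, d6 = -8, d12 = -10 mmHg, with two fills from month 6 for each fill from month 1:

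- 15% filled (f6 = 0.10, f1 = 0.05): 0.10 × 2 + 0.05 × 6 = 0.5; reported change -9.5.
- 30% filled (f6 = 0.20, f1 = 0.10): 0.20 × 2 + 0.10 × 6 = 1.0; reported change 0.7 × (-10) + 0.2 × (-8) + 0.1 × (-4) = -9.0.
- 45% filled (f6 = 0.30, f1 = 0.15): 0.30 × 2 + 0.15 × 6 = 1.5; reported change -8.5.

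A cruder bound: if 10% to 30% of the 1-year values are off-time and differ from the true 1-year value by 2 to 6 mmHg on average, the mean shifts by 0.1 × 2 = 0.2 to 0.3 × 6 = 1.8 mmHg.

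**4. Direction.** Exchange the last two values, so that the effect wanes (d6 = -10, d12 = -8). At 30% filled, the error is 0.20 × (-2) + 0.10 × 4 = 0. If only month 6 supplies substitutes (f6 = 0.20, f1 = 0), it is -0.4 mmHg, an overstatement of the fall. The sign depends on the trajectory and on which visits supply the substitutes.

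**The case against.** The best counter-argument is context. The same paragraph draws the data from routine follow-up at 1 month, 6 months and 1 year, and the schedule table lists a separate home BP at each. On that reading, the sentence only picks the best-timed record for a visit that took place. This is a plausible account of the intent, and a reader who infers that sites are ordered to fill every absent visit goes further than the text. But the text does not confine the rule to visits that took place, and it says nothing about an absent one, so sites can apply it either way.

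A reader might also infer that readings taken years late will commonly stand as 1-year values. The documents do not support that. The calendar limits it for prospective patients, and a retrospective patient whose only home reading came at 5 years should usually fail the condition on missing data. That condition, however, is a judgement by the investigator about the record as a whole. It is not a test on the 12-month home SBP.

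Follow-up dates are recorded, and a statistical analysis plan could use them to exclude off-time values. This is a real safeguard if the date entered is that of the reading; the protocol does not say so, and none of its rules uses the date. Tracing of patients lost to follow-up may recover some information, but it does not create a 12-month reading that was never taken.

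Finally, the size rests wholly on assumed inputs, and the primary objective is descriptive, with no threshold that the shift would cross. Both points stand.

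**Conclusion.** The point holds in a limited form. The protocol fixes an unbounded selection rule for the primary value. Where no home reading exists near 12 months, the literal rule lets a reading from another time stand as the 1-year value and hides that it was missing. The routine-visit wording, the retrospective condition and the recorded date reduce how often this happens and how hard it is to detect, but none of them sets a limit.

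The 0.5 to 1.5 mmHg range is an illustration that depends on the assumed trajectory, 15% to 45% missing, and the 2:1 split between month-6 and month-1 substitutes. It would be wrong to infer that the registry will understate the 1-year effect by about 1 mmHg, since the error can vanish or change sign. Nor does it follow that the 12-month visit will look fully complete, because that would need every patient without a 12-month value to have another post-procedure home reading. The masking of missing values itself does not depend on the assumed effect sizes.

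**What to change.** Amend the selection rule in the Data collection section as follows:

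- Define a window around each time point in advance, with no overlap between windows.
- Within a window, enter the reading closest to the target day.
- If the window holds no reading, leave the visit missing.
- Use each reading for one visit only.
- Enter the date of the reading itself, and check it against the window in the eCRF.

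The sponsor should choose the widths, as the document gives no basis for particular ones. The secondary objectives also name 3 months, which the collection times do not include, so the widths should be set with that time point in view.

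The cost is a short protocol amendment and an eCRF date check. The change concerns data entry only. The downside is that more 12-month values will be shown as missing. If the 12-month window runs past month 12, the sponsor should also check that the April 2028 end of follow-up covers the last included patients, who reach exactly 12 months then. Any extension would be a separate change to the schedule.
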